9.1.1.5 Visit 4 (Day 15 [+3 Days]): End of Pilot or Pivotal Phase/Withdrawal

This visit will occur 14 (+3) days after Visit 2 or earlier if the patient withdraws from the pilot or pivotal phase of the trial. The following will be collected/assessed:

- Concomitant medication review (Section 9.2.5).
- Physical examination (Section 9.2.6).
- Vital signs (Section 9.2.7).
- ECG (prior to the day's first dose of IMP; Section 9.2.8).
- Video-EEG (Section 9.2.9).
- Clinical laboratory samples (blood and urine [if possible]; Section 9.2.10) for:
 - Serum biochemistry.
 - Hematology.
 - Urinalysis.
- **Pivotal phase only**: PK blood sampling (prior to the day's first dose of IMP, provided the risk/benefit outcome is favorable in the investigator's opinion; Section 9.2.11).
- CGIC (Section 9.2.12.1).

- PGIC (Section 9.2.12.2).
- Caregiver diary review (Section 9.2.13) for:
 - Spasm/seizure information.
 - IMP usage.
 - Changes in concomitant AEDs.
 - Usage of rescue medication.
 - AEs.
- AEs (Section 12).

Patients will take their IMP in the clinic with an additional ECG assessment between 3 and 5 hours postdose (Section 9.2.8). For patients involved in the pivotal phase of the trial, a further PK blood sample will be taken, provided the risk/benefit outcome is favorable in the investigator's opinion (Section 9.2.11). If PK blood samples are collected, the investigator must note the sampling times and the dosing times of the IMP and of any concomitant AEDs taken that day and the previous day. All IMP will be collected and compliance reviewed.

Patients who have successfully completed the pilot or pivotal phase will have the opportunity to receive GWP42003-P during the subsequent OLE phase at Visit 4. Patients from the pilot phase who enter the OLE phase will remain at the target dose which was reached during the pilot phase. Patients from the pivotal phase who enter the OLE phase will receive sufficient blinded IMP for tapering along with sufficient OLE IMP (GWP42003-P) for simultaneous titration and subsequent dosing for 2 weeks. All patients in the pivotal phase who enter the OLE phase will transition to the target dose of GWP42003-P (in a blinded manner; Section 8.1.2) and may continue at this dose, or the highest tolerated dose up to 40 mg/kg/day, for the remainder of the OLE phase. Following Visit 4, daily safety checks will be made during the first week of GWP42003-P dosing.

For patients who withdraw early, the IVRS/IWRS will be contacted to confirm withdrawal from the trial. Patients who opt not to enter the OLE phase or who withdraw from the pilot or pivotal phase early should begin the taper period, if possible (Section 9.1.3), and sufficient IMP will be dispensed.

9.1.2 Open-label Extension Phase

The OLE phase will last for a maximum of 1 year.

During the OLE phase, GWP42003-P may be discontinued by the investigator if:

EudraCT Number: 2015-004904-50

Protocol V3 20Sep16

• The patient has become spasm-free, as determined by clinical assessment by the investigator.

OR

• The patient is not perceived to be receiving any benefit from GWP42003-P, as determined by clinical assessment by the investigator.

For any patients who have their IMP discontinued by the investigator, the IVRS/IWRS will be contacted to confirm IMP discontinuation. All patients should commence the taper period, if possible (Section 9.1.3), and sufficient IMP will be dispensed if required.

If the investigator decides to discontinue GWP42003-P following resolution of spasms, the parent(s)/legal representative will be encouraged to allow the patient to remain in the trial to complete the remaining assessments. The investigator must contact the GW medical monitor to discuss the discontinuation process, including the subsequent assessments to be conducted.

If the investigator decides to discontinue GWP42003-P because the patient is not perceived to be receiving any benefit from GWP42003-P, the patient will **not** be asked to complete the remaining trial assessments and will be withdrawn from the trial as per Section 10 (withdrawal to be registered in the IVRS/IWRS).

Patients who have not demonstrated complete resolution of spasms but are perceived to be receiving some benefit from GWP42003-P may remain in the OLE and receive other concomitant medications during the OLE phase. The option of withdrawal from the trial will be discussed with the caregiver at each visit.

In cases of relapse, patients may restart IMP only if ALL of the following criteria are fulfilled:

- The patient had their IMP discontinued by the investigator due to resolution of spasms.
- The patient has remained in the trial to complete the remaining assessments.
- The decision to restart IMP is discussed with the GW medical monitor.

The IVRS/IWRS will then be contacted to confirm restart of IMP. Patients restarting IMP will re-titrate to their target dose of GWP42003-P and may continue at this dose, or the highest tolerated dose up to 40 mg/kg/day, for the remainder of the OLE phase. The next scheduled clinic visit will then be performed according to the Schedule of Assessments (APPENDIX 1).

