5.3.4 Investigational Medicinal Product Accountability

The investigator has overall responsibility for the accountability of all used and unused IMP. A drug accountability record for the IMPs must be kept current and must contain:

- Study code.
- PRN, treatment number, date of receipt, and quantity of IMP received.
- Patient's trial identification and/or treatment number.
- Date and quantity of IMP dispensed.
- The initials of the dispensing/dosing party.
- Date and quantity of IMP returned to the investigator.
- IMP expiry dates.

IMP will be dispensed at Visits 2, 4, 6–11, and for the taper period, if necessary. Patients will be asked to return all IMP (used and unused) at each relevant visit (Visits 4, 6–12, and the end of taper period visit, if applicable). The site will check the returned IMP against the usage recorded in the paper diary. Any discrepancies

EudraCT Number: 2015-004904-50

Protocol V3 20Sep16

will be discussed with the patient's caregiver at the time of the visit and documented accordingly within the patient's source documents.

The investigator must inform GW promptly of all missing or unaccountable IMP.

A record of returned IMP must be completed and included in the shipment of used and unused IMP to the relevant drug distribution depot. At the end of the trial, a record/statement of reconciliation must be completed and provided to GW.

These inventories must be made available for inspection by an authorized GW representative and local officials or regulatory agency inspectors.

Please refer to the separate pharmacy manual for more detailed information on the IMP.

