Patients from the pivotal phase who enter the OLE will taper their blinded IMP while simultaneously titrating their OLE IMP (GWP42003-P) over 4 days according to the titration regimen, an example titration regimen up to 40 mg/kg/day over 4 days is shown in Table 8.1.2-2. No further titration will be required for patients in the pilot phase; they will remain on the same GWP42003-P dose going into the OLE phase. Daily safety checks will be made during the first week of OLE IMP dosing. GWP42003-P may be discontinued at any time during the OLE phase, at the discretion of the investigator (see Section 9.1.2).

Table 8.1.2-2 Example Titration Regimen: Transition to the OLE Phase (Pivotal Phase Only)						
Day	Blinded IMP Dosage ¹	OLE IMP Dosage ¹	Total Daily IMP Dose (Patients Randomized to Placebo) ²	Total Daily IMP Dose (Patients Randomized to GWP42003-P) ²		
15	20 mg/kg (am/pm)	0	0	40 mg/kg		
16	15 mg/kg (am/pm)	5 mg/kg (am/pm)	10 mg/kg	40 mg/kg		
17	10 mg/kg (am/pm)	10 mg/kg (am/pm)	20 mg/kg	40 mg/kg		
18	5 mg/kg (am/pm)	15 mg/kg (am/pm)	30 mg/kg	40 mg/kg		
19 onwards	0	20 mg/kg (am/pm)	40 mg/kg	40 mg/kg		

Volumes of IMP to be taken each day will be calculated using the patient's weight and the required dose.

²Patients may taper to and remain on a lower dose if unable to tolerate the target dose.

²Patients may taper to and remain on a lower dose if unable to tolerate the target dose.

EudraCT Number: 2015-004904-50

Protocol V3 20Sep16

Following the end of treatment, all patients will commence a taper period (tapering 10% per day for 10 days). Patients who withdraw early should also begin the taper period following the withdrawal visit (unless continued dosing is not possible due to an AE). Patients who discontinue IMP during the OLE phase should also begin the taper period following the investigator's decision to discontinue. The IVRS/IWRS will generate the patient's daily IMP dosing volumes for the 10-day taper period.

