9.1.1.3 Daily Safety Checks (Day 2 to Day 7 [Inclusive])

Safety checks will be made daily (including weekends, where possible) from Day 2 to Day 7 (inclusive). Safety checks can be conducted by telephone (where applicable they will be incorporated into scheduled visits, e.g., Visit 3 [Day 4]). During each safety check, caregivers will be asked about the following, along with confirmation that the relevant details have been recorded in the caregiver diary:

- Spasm/seizure information.
- Changes in concomitant AEDs.
- Usage of rescue medication.
- AEs.

Confirmation that the safety check has taken place will be recorded in the CRF.

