9.1.2.1 Daily Safety Checks (Day 16 to Day 22 [Inclusive])

Safety checks will be made daily (including weekends, where possible) from Day 16 to Day 22 (inclusive). Safety checks can be conducted by telephone (where applicable they will be incorporated into scheduled visits, e.g.. Visit 5 [Day 19]). During each safety check, caregivers will be asked about the following, along with confirmation that the relevant details have been recorded in the caregiver diary:

- Spasm/seizure information.
- Changes in concomitant AEDs.
- Usage of rescue medication.
- AEs.

Confirmation that the safety check has taken place will be recorded in the CRF.

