10 WITHDRAWAL

In accordance with the Declaration of Helsinki⁵⁶, the International Conference on Harmonisation (ICH) Tripartite Guideline for GCP Topic E6(R1)⁵⁷, the FDA regulations relating to GCP and clinical trials^{58,59,60}, the EU Clinical Trials Directive⁶¹, the EU GCP Directive⁶² and/or other applicable regulations, a patient has the right to withdraw from the trial at any time and for any reason, with no obligation to provide a reason, and without prejudice to his or her future medical care by the physician or at the institution.

The patient must be withdrawn from the trial if any of the following apply:

- Any issue with eligibility criteria that is considered to potentially compromise the safety of the patient.
- Administrative decision by the investigator, GW, or a regulatory authority.
- Protocol deviation that is considered to compromise potentially the safety of the patient.
- Withdrawal of the patient's parent(s)/legal representative consent.
- QTcB of 500 msec or greater on ECG, or a shift from baseline QTcB of 60 msec or greater.

Note: Prior to withdrawal for the QTcB shifts noted above, the investigator should repeat the ECG three times and contact the GW medical monitor. If the above QTcB criteria are confirmed, the patient must be withdrawn from the trial.

- Lost to follow-up.
- ALT or AST > 3 × ULN with the appearance of fatigue, nausea, vomiting, right upper quadrant pain or tenderness, fever, rash, and/or eosinophilia (> 5%).
- ALT or AST $> 8 \times ULN$.
- ALT or AST $> 5 \times ULN$ for more than 2 weeks.
- ALT or AST $> 3 \times$ ULN and (TBL $> 2 \times$ ULN or INR > 1.5).

Note: Prior to withdrawal for the transaminase elevations noted above, the Investigator may choose to confirm the transaminase elevations by repeating the following laboratory tests within 24 to 48 hours: ALT, AST, TBL, INR, % eosinophils, gamma glutamyl transferase and alkaline phosphatase. **Should the above**

EudraCT Number: 2015-004904-50

Protocol V3 20Sep16

transaminase elevation criteria be confirmed, the patient must be withdrawn from the trial.

Patients may also be withdrawn from the trial for any of the following:

- Any other issue with eligibility criteria (non-safety related).
- Any requirement to increase the dose of concomitant AED(s) or to add in new AED(s) during the pilot or pivotal phase.

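### A restart after relapse triggers no daily safety check, ECG or laboratory test during re-titration to as much as 40 mg/kg/day

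*Protocol*

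**What the plan says.** **Restart.** Under Protocol Section 9.1.2 a relapsing infant may restart only if three conditions all hold: the investigator stopped the drug because spasms resolved, the infant stayed in the trial for the remaining assessments, and the decision to restart is discussed with the medical monitor. Then "Patients restarting IMP will re-titrate to their target dose of GWP42003-P and may continue at this dose", or at the highest tolerated dose up to 40 mg/kg/day. The follow-up instruction is: "The next scheduled clinic visit will then be performed according to the Schedule of Assessments" (Appendix 1).

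**Discontinuation.** When the drug is stopped for resolution, the same section requires a conversation: "The investigator must contact the GW medical monitor to discuss the discontinuation process, including the subsequent assessments to be conducted".

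**First titration.** Daily checks run from Day 2 to Day 7 (Section 9.1.1.3). Visit 3, on Day 4, has vital signs, laboratory tests and ECGs before and after the dose (Section 9.1.1.4).

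**OLE entry.** Daily checks run from Day 16 to Day 22 (Section 9.1.2.1). Visit 5, on Day 19, has vital signs, ECG and laboratory tests (Section 9.1.2.2). Pilot infants get all of this although their dose does not change: "No further titration will be required for patients in the pilot phase; they will remain on the same GWP42003-P dose" (Section 8.1.2).

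**Supply.** Section 5.3.4: "IMP will be dispensed at Visits 2, 4, 6–11, and for the taper period, if necessary".

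**The concern.** The protocol treats the climb to target dose as a period to watch. Section 3.3.1 gives rapid titration as the reason for keeping pilot infants in hospital, and both planned dose transitions have daily contact and an early test visit. A restart takes an infant from no drug back to target without either.

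What is at stake is the safety of the individual infant. Several mandatory withdrawal rules in Section 10 need no symptom: "QTcB of 500 msec or greater on ECG, or a shift from baseline QTcB of 60 msec or greater"; ALT or AST above 8 × ULN; and ALT or AST above 3 × ULN together with total bilirubin above 2 × ULN or INR above 1.5. A diary entry or a telephone call cannot reveal these; they operate only if an ECG or blood sample is taken.

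The background treatment may also differ from that at first titration. Section 8.2 bars antiepileptic increases and additions in the pilot and pivotal phases but allows them in the OLE after discussion with the medical monitor. The same section warns of drug interactions and of a high hepatotoxicity risk with valproate in this population.

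**Working it through.** **1. Monitoring attached to each dose transition**

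| Transition | Daily checks | ECG and laboratory tests tied to it |
|---|---|---|
| First titration | Days 2–7: 7 − 2 + 1 = 6 | Visit 3, Day 4 |
| OLE entry | Days 16–22: 22 − 16 + 1 = 7 | Visit 5, Day 19 |
| Restart after relapse | 0 | none |

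Visits 3 and 5 are counted from Visit 2, so they cannot recur at a restart.

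**2. Could other text fill the gap?**

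- Section 8.1.2 and an Appendix 1 footnote describe the checks as covering the first week of OLE dosing. Section 9.1.2.1 fixes this as Days 16–22, and Section 9.1.1.5 ties it to Visit 4. It means OLE entry.
- Weekly calls (Section 9.1.4.1) include no ECG or blood test and stop at the next scheduled visit for infants who stay in the trial off drug. They could overlap a restart between visits, but not one supplied at that next visit.
- End-of-taper ECG and laboratory tests (Section 9.1.3.1), and the tests at a visit where restart supply is given, come before re-exposure.
- Extra ECGs (Section 9.2.8) are taken if clinically indicated. Dose suspension (Section 8.1.2) follows an unacceptable adverse event. Repeat liver tests (Section 12.7) follow an abnormal result already in hand.

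None of these schedules a test because a restart has occurred.

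**3. Longest wait for the next scheduled ECG and laboratory tests**

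The inputs are the visit days and windows in Section 4.1. Nominal gap = next visit day − this visit day. Shortest = (next day − its window) − (this day + its window). Longest = (next day + its window) − (this day − its window).

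| Last visit | Next visit | Nominal gap | Range with windows | Supply stated in Sections 9.1.2.3–9.1.2.8 |
|---|---|---|---|---|
| 6 (Day 29 ± 3) | 7 (Day 43 ± 3) | 14 | 8–20 | 2 weeks |
| 7 (Day 43 ± 3) | 8 (Day 71 ± 3) | 28 | 22–34 | 4 weeks |
| 8 (Day 71 ± 3) | 9 (Day 127 ± 7) | 56 | 46–66 | 8 weeks |
| 9 (Day 127 ± 7) | 10 (Day 211 ± 7) | 84 | 70–98 | 12 weeks |
| 10 (Day 211 ± 7) | 11 (Day 295 ± 7) | 84 | 70–98 | 12 weeks |
| 11 (Day 295 ± 7) | 12 (Day 379 ± 7) | 84 | 70–98 | 12 weeks |

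The nominal gaps reproduce the stated weeks of supply. They are upper limits, reached when the restart begins at the earlier visit. Section 9.1.2 does not confine restarts to visits, so the wait can be anything from a few days up to the interval shown.

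**4. What an end-of-re-titration test would change**

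Section 9.1.2 gives no length for re-titration. Assume the four-day example in Section 8.1.2. For a restart at Visit 9, 10 or 11, target is reached three days later and 84 − 3 = 81 days remain to the next scheduled tests; with the test a day later, 84 − 4 = 80 remain. The added test covers the titration period and leaves the later interval almost as it was.

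**The case against.** The other side has substantial points.

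- **The 84 days is not specific to restarts.** Every infant who leaves Visit 9, 10 or 11 on drug has the same interval. This stands in full. A reader might infer that the restart rule creates a 12-week monitoring gap; the documents do not support that.
- **Timing is open.** Three of the six visits from Visit 6 to Visit 11 start an 84-day interval, but that is not a probability that a restart faces one. A restart between visits could fall just before a scheduled ECG and blood test. This also stands.
- **The infant is not drug-naive.** Earlier titration was monitored, and the drug was stopped for resolution rather than intolerance. The OLE-entry checks sit in a schedule shared with pivotal infants, some of whom do titrate then. So it does not follow that the protocol ranks an unchanged dose as riskier than a restart. Nor do the documents show that re-titration after earlier exposure carries a QTc or hepatic risk that demands a fixed test. What remains is that an infant returning from no drug to target is titrating, and neither document gives a reason for dropping the checks.
- **Medical monitor contact is compulsory.** It is, so it would be wrong to say that restarts are ungated. But the stated content at restart is the decision itself; assessments are named only at discontinuation. Tests may be agreed, but none is required.
- **Symptoms can prompt a test.** One liver criterion in Section 10 pairs ALT or AST above 3 × ULN with symptoms, and a diary entry or call could lead to that blood test. This does not help with the criteria that need no symptom.
- **A further blood draw has a cost.** Section 9.2.10 warns that more blood tests may be unsafe within a month of a trial draw. That makes the laboratory part of any remedy more debatable than the telephone checks.

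**Conclusion.** The point holds in a limited form. A restart triggers no daily check, ECG or laboratory test, so re-titration to as much as 40 mg/kg/day is scheduled with less monitoring than first titration (six daily checks and a Day 4 test visit) or OLE entry (seven and a Day 19 test visit). The wait for the next scheduled tests ranges from a few days to the full inter-visit interval; the restart-specific part is the period during and at the end of re-titration.

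The number affected is likely to be small. SAP Section 4.1 gives 9 pilot patients, SAP Section 5 says that only pilot patients were included, and a restart needs resolution, discontinuation, continued participation and relapse. The documents give no count of restarts. A reader might infer that the relapse results or other OLE endpoints are compromised; nothing here touches an endpoint or a SAP summary. The change is worth making because the telephone checks are cheap and already defined.

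The conclusion assumes that the first-week wording means OLE entry, as Section 9.1.2.1 indicates. The 80- and 81-day figures also assume a four-day re-titration.

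**What to change.** Add to Section 9.1.2 after the re-titration sentence, and as a footnote to Appendix 1:

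> After any restart, the daily telephone safety checks of Section 9.1.2.1 will be made for the first 7 days of re-titration. Vital signs, ECG and, within the limits and precautions of Section 9.2.10, clinical laboratory tests as at Visit 5 will be done at the end of re-titration (+1 day), unless a scheduled visit with these tests falls then.

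The telephone checks are the core of the change. The cost per restart is seven calls and, where no scheduled visit coincides, one short visit with an ECG and a blood draw. The draw must stay within 3 mL/kg per 24 hours and 50 mL per 8 weeks and respect the one-month caution. For a restart at a dispensing visit with a four-day re-titration, it falls about 4 days after that visit's draw, the spacing the protocol already uses between Visit 4 and Visit 5 (19 − 15 = 4).

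The addition has limits. One test cannot establish ALT or AST above 5 × ULN for more than 2 weeks. INR may be missing, because prothrombin time is only an additional laboratory parameter in Section 9.2.10. The 12-week visit interval is unchanged. No SAP change is needed.

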9.1.2.1 Daily Safety Checks (Day 16 to Day 22 [Inclusive])

Safety checks will be made daily (including weekends, where possible) from Day 16 to Day 22 (inclusive). Safety checks can be conducted by telephone (where applicable they will be incorporated into scheduled visits, e.g.. Visit 5 [Day 19]). During each safety check, caregivers will be asked about the following, along with confirmation that the relevant details have been recorded in the caregiver diary:

- Spasm/seizure information.
- Changes in concomitant AEDs.
- Usage of rescue medication.
- AEs.

Confirmation that the safety check has taken place will be recorded in the CRF.

9.1.2.2 Visit 5 (Day 19 [+1 Day])

This visit will occur 18 (+1) days after Visit 2. The following will be collected/assessed:

- Concomitant medication review (Section 9.2.5).
- Vital signs (Section 9.2.7).
- ECG (Section 9.2.8).
- Clinical laboratory samples (blood and urine [if possible]; Section 9.2.10) for:
 - Serum biochemistry.
 - Hematology.
 - Urinalysis.
- Caregiver diary review (Section 9.2.13) for:
 - Spasm/seizure information.
 - IMP usage.
 - Changes in concomitant AEDs.
 - Usage of rescue medication.
 - AEs.
- AEs (Section 12).

All patients will take their IMP in the clinic. For patients transitioning from the pivotal phase to the OLE a PK blood sample will be taken, provided the risk/benefit outcome is favorable in the investigator's opinion (Section 9.2.11). If a PK blood sample is collected, the investigator must note the sampling time and the dosing times of IMP and of any concomitant AEDs taken that day.

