Investigational Medicinal Product:	Dose (pivotal phase): Patients will titrate the IMP to the target dose level over 4 days and will continue at this dose, or the highest tolerated dose up to the target dose level, for the remainder of the blinded treatment phase.
Formulation, Mode of Administration, Dose and Regimen (continued)	Dose (OLE phase): Patients will remain on the same dose (pilot phase) or will transition to the target dose of GWP42003-P, or the highest tolerated dose up to 40 mg/kg/day, over 4 days (10 mg/kg/day), in a blinded manner (pivotal phase). Patients may continue at this dose for the remainder of the OLE phase. GWP42003-P may be discontinued at any time during the OLE phase, at the discretion of the investigator, but patients who have become spasm-free and have resolution of hypsarrhythmia will be encouraged to continue to attend all subsequent clinic visits. Dosage: IMP is taken twice daily (morning and evening), maintaining consistency with regard to feeds/meals and other concomitant medications, and can be taken with other concomitant medications as directed by the investigator. In the event that the IMP is poorly tolerated, dosing may be changed to 3 times daily (while keeping the equivalent total daily dose), following approval by the GW medical monitor. The recommended dosing intervals are:
	 12-hourly (8-hourly minimum) for twice daily dosing. 6-hourly (minimum) for 3 times daily dosing.
Control Group	The control group in the pivotal phase will receive equivalent dosing volumes of matching placebo.
Procedures	Pilot and Pivotal Phase
	Visit 1 (Day -7 to Day -1): Screening
	The following will be collected/assessed:
	Informed consent.
	Eligibility criteria.
	Patient demographics.
	Full medical history.
	Concomitant medication review.
	• Physical examination (including length [height], body weight, and head circumference).
	• Vital signs (including supine blood pressure).
	• ECG.
	• Video-EEG (8–24 hours in duration).
	• Clinical laboratory samples (blood and urine [if possible]) for:
	 Serum biochemistry.
	- Hematology.

EudraCT Number: 2015-004904-50

Protocol V3 20Sep16

Urinalysis.

Procedures (continued)

To minimize the volume of blood required, serum biochemistry and hematology results from samples analyzed up to 3 days prior to Visit 1 may be used.

- AEs.

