9.1.2.3 Visit 6 (Day 29 [±3 Days])

This visit will occur 28 (±3) days after Visit 2. Collection of Visit 6 assessments earlier than Day 29 (i.e., on Day 26, 27, or 28) must only occur if there have been no witnessed spasms over the preceding 48 hours (minimum). The following will be collected/assessed:

- Concomitant medication review (Section 9.2.5).
- Physical examination (Section 9.2.6).
- Vital signs (Section 9.2.7).
- ECG (Section 9.2.8).
- Video-EEG (Section 9.2.9).
- Clinical laboratory samples (blood and urine [if possible]; Section 9.2.10) for:
 - Serum biochemistry.
 - Hematology.
 - Urinalysis.
- CGIC (Section 9.2.12.1).
- PGIC (Section 9.2.12.2).
- Caregiver diary review (Section 9.2.13) for:
 - Spasm/seizure information.
 - IMP usage.
 - Changes in concomitant AEDs.
 - Usage of rescue medication.
 - AEs.
- AEs (Section 12).

All IMP will be collected and compliance reviewed. Patients will then receive sufficient IMP for 2 weeks' dosing.

EudraCT Number: 2015-004904-50

Protocol V3 20Sep16

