2.1.3 Addition of a Pilot Phase to Confirm Safety

Due to the lack of safety data in infants under 2 years of age, safety will be confirmed in a small group of patients in a hospital environment (pilot phase) before proceeding to the pivotal investigations. Therefore, the trial will be performed as 2 separate phases (pilot and pivotal) which will be run sequentially. All patients in the pilot phase will receive GWP42003-P (open-label) while all patients in the pivotal phase will be randomly allocated to GWP42003-P (1 of 2 dose levels) or matching placebo in a double-blind manner. As infants younger than 6 months are particularly vulnerable, all patients in the pilot phase will be over 6 months of age. The pivotal phase will only be enrolled after the DSMC

EudraCT Number: 2015-004904-50 Protocol Amendment 1 V1 31May16

has reviewed data from the pilot phase and has confirmed that there are no safety issues.

Due to the rapid titration of the investigational medicinal product (IMP), all patients in the pilot phase will remain in the clinic as inpatients during the 4-day titration period. In both phases, compulsory clinic-based assessments will take place at the end of the titration period (i.e., Day 4) and OLE transition period (i.e., Day 19). In addition, daily safety checks will be made during the first week of IMP dosing during the pilot and pivotal phases (i.e., Days 1–7) and during the first week of OLE IMP dosing (i.e., Days 16–22).

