2.11 Minor Corrections and Clarifications

The following minor corrections/clarifications have been made to the protocol:

- Only patients who complete the pilot or pivotal phase will have the opportunity to continue to the OLE phase; those who withdraw early are ineligible.
- Since absorption of topical mammalian target of rapamycin (mTOR) inhibitors is lower than oral formulations, only oral mTOR inhibitors may not be used.
- The eligibility criterion regarding breastfeeding has been combined with the criterion regarding abstention.
- The physical description of the IMP has been updated to "clear, colorless to yellow solution".
- The information to be recorded in the paper diary has been added to the synopsis for clarity.
- The full 4-week safety follow-up period concludes with the safety follow-up visit.
- Caregivers will record IMP intake in the paper diary but will not be required to record the volume of IMP administered on each treatment day.
- The assessments listed as bullet points in Section 9.1.1.2 (Visit 2 [Day 1]) must be conducted prior to receiving the first dose of IMP.

- The timings of any PK blood draws must be recorded, as well as IMP dosing time and the timing of concomitant AEDs and feeds/meals around the time of PK sampling.
- Vital signs and clinical laboratory samples must be assessed/collected on Day 4.
- In the OLE phase, all visit days and visit windows are in relation to Visit 2.
- Medical history includes prior and current seizures/spasms.
- The laboratory manual should be referred to for analysis of clinical laboratory samples.
- Since local laboratories will be used, all laboratory results must be documented on the case report form.
- The dose and number of times rescue medication is given each day will be recorded in the paper diary.
- The patient's parent(s)/legal representative would voluntarily withdraw the patient (rather than the patient withdrawing themself, due to their age).
- All statistical analyses will be conducted at the 5% level of significance.
- The end of the evaluable period for the OLE phase is defined as the last day on which a study-related assessment was undertaken during the OLE phase as opposed to the last day on which the study IMP was taken.
- Participation in the trial would not delay initiation with the next recognized IS therapy if the patient had failed all recognized IS therapies at enrollment.

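### Visit 5 is counted from Visit 2, so after a Day 17 or 18 Visit 4 the end-of-transition ECG and laboratory check precedes full open-label dose for former placebo infants

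*Protocol*

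**What the plan says.** Section 9.1.1.5 places Visit 4 as follows: "This visit will occur 14 (+3) days after Visit 2", so Days 15 to 18. Drug for the transition is handed over at that visit. Pivotal patients going on to the OLE "will receive sufficient blinded IMP for tapering along with sufficient OLE IMP".

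Section 8.1.2 says these patients "will taper their blinded IMP while simultaneously titrating their OLE IMP (GWP42003-P) over 4 days". Its example, Table 8.1.2-2, shows no OLE drug on Day 15, then 10, 20, 30 and 40 mg/kg/day on Days 16 to 19.

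Section 9.1.2.2 schedules Visit 5, which includes vital signs, ECG, laboratory tests and a PK sample: "This visit will occur 18 (+1) days after Visit 2". The next ECG and laboratory tests are at Visit 6, 28 (±3) days after Visit 2 (Section 9.1.2.3). If spasms have been witnessed in the previous 48 hours, Visit 6 may not be brought forward before Day 29.

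The Amendment 1 rationale, used here only as evidence of intent, says in 2.1.3 that "compulsory clinic-based assessments will take place at the end of the titration period (i.e., Day 4) and OLE transition period (i.e., Day 19". In 2.11 it records the anchor: "In the OLE phase, all visit days and visit windows are in relation to Visit 2".

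**The concern.** Two clocks are in use. The transition runs from the actual Visit 4, and the visit meant to check its end runs from Visit 2. They agree when Visit 4 is on Day 15 and drift apart as Visit 4 moves later within its permitted window. No text moves Visit 5 to compensate.

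The first titration is handled differently. It starts at Visit 2, and Visit 3 is counted from Visit 2, so Visit 3 falls on the first full-dose day of Table 8.1.2-1 (Day 4) or the day after.

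At stake is safety monitoring. Infants coming from placebo meet active drug for the first time and climb quickly. The withdrawal rules in Section 10 on QTcB and transaminases depend on ECG and laboratory results, and Visit 5 is the only scheduled source of these between Visit 4 and Visit 6.

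**Working it through.** **Inputs.** Visit 4 on Days 15 to 18 (Section 9.1.1.5). Visit 5 on Day 19 or 20 (Section 9.1.2.2). Visit 6 on Days 26 to 32 (Section 9.1.2.3). OLE dose of 0, 10, 20, 30 and 40 mg/kg/day on days 0 to 4 after Visit 4 (Table 8.1.2-2).

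**Formulas.** Full-dose day = Visit 4 day + 4. OLE dose at Visit 5 = 10 × (Visit 5 day − Visit 4 day), capped at 40.

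**The plan's own figure.** Visit 4 on Day 15 gives 15 + 4 = Day 19 and 10 × (19 − 15) = 40 mg/kg/day, as in the table.

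**Whole window.** Former Low Dose infants are shown under three assumptions: 20 mg/kg/day of blinded drug, tapered 15, 10, 5, 0, and an OLE target of 40. Their totals on days 1 to 4 after Visit 4 are then 25, 30, 35 and 40.

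| Visit 4 | Full dose | Former placebo, mg/kg/day, Visit 5 on Day 19 / 20 | Former Low Dose (conditional), Day 19 / 20 |
|---|---|---|---|
| Day 15 | Day 19 | 40 / 40 | 40 / 40 |
| Day 16 | Day 20 | 30 / 40 | 35 / 40 |
| Day 17 | Day 21 | 20 / 30 | 30 / 35 |
| Day 18 | Day 22 | 10 / 20 | 25 / 30 |

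After a Day 17 or 18 Visit 4, no in-window Visit 5 reaches full dose. After a Day 16 Visit 4, only Day 20 does. Infants already on 40 mg/kg/day of active drug stay at 40 throughout and are unaffected.

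**Wait from full dose to Visit 6.**
- Full dose on Day 21: 26 − 21 = 5 to 32 − 21 = 11 days.
- Full dose on Day 22: 26 − 22 = 4 to 32 − 22 = 10 days.
- If spasms persist, Visit 6 is on Days 29 to 32, and the waits are 8 to 11 and 7 to 10 days.

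**Sensitivity to the example table.** With a 4-day transition the day count is the same at any target. If a lower target were reached in fewer 10 mg/kg/day steps, the gap shrinks:
- Target 30: full dose at Visit 4 + 3, so Days 18, 19, 20 and 21. Only a Day 18 Visit 4 has no full-dose Visit 5.
- Target 20: full dose at Visit 4 + 2, so Days 17, 18, 19 and 20. A Day 18 Visit 4 is covered if Visit 5 is on Day 20.

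**The case against.** **The Visit 2 anchor was chosen on purpose, and Section 9.1.2.2 does not itself call Visit 5 an end-of-transition check.** Both are true, so this is a design choice open to improvement. The purpose does not rest on the amendment rationale alone, though: the full-dose row of Table 8.1.2-2 begins on Day 19, the nominal Visit 5 day. Nothing in the anchoring rule considers a late Visit 4.

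**Infants are not left unwatched.** This stands. Section 9.1.2.1 schedules daily safety checks to Day 22, so even after a Day 18 Visit 4 there is planned contact on the first full-dose day. The checks may be by telephone and include no ECG or laboratory tests. Section 9.2.8 allows extra ECGs when clinically indicated, and Section 8.1.2 allows dose changes for adverse events. Visit 5 still gives one ECG and laboratory check on active drug.

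**Even an on-time Visit 5 does not guarantee a full-dose test.** This also stands. Section 9.1.2.2 does not time the ECG or blood draw against the dose, so tests before the Day 19 morning dose would reflect the 30 mg/kg/day of Day 18. A late Visit 4 makes the shortfall certain and larger.

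**Stronger readings the documents do not support.**
- A reader might infer that all former Low Dose infants are affected. The synopsis dosing entry and Section 9.1.1.5 speak of one target dose and favour a common target. The synopsis design text and Section 4.1 use the possessive (their target), which could mean an arm-specific dose. On that reading Low Dose infants have no dose rise in the transition.
- A reader might infer that the protocol forgets to move the daily checks. Sections 8.1.2 and 9.1.1.5 and Appendix 1 footnote 2 already tie them to the first week of OLE dosing. Only the Day 16 to 22 labels fail to follow.
- A reader might infer that reported results are affected. SAP Section 5 says only pilot patients were included, and they have no transition.

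**Conclusion.** The point holds for former placebo infants when Visit 4 is on Day 17 or 18 and the transition takes 4 days. Their only scheduled ECG and laboratory check before Visit 6 is then done at 10 to 30 mg/kg/day on the 40 mg/kg/day example, and the next is 4 to 11 days after full dose. It extends to former Low Dose infants only under a common OLE target of 40 mg/kg/day, with 25 to 35 mg/kg/day at Visit 5 under the taper assumed above.

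The conclusion rests on the example table; the DSMC sets the High Dose Level, and the OLE target may differ. The documents do not say how often Visit 4 would be late. The 64 planned placebo infants (plus 64 Low Dose infants on the common-target reading) are a ceiling, not an estimate of how many would be affected. This is a minor weakness in the written pivotal-to-OLE schedule, worth correcting because correction is cheap.

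**What to change.** For pivotal patients entering the OLE, set Visit 5, with its ECG, laboratory tests and PK sample, at 4 (+1) days after the actual Visit 4, as a stated exception to the Visit 2 anchor. Pilot patients keep Day 19 (+1). Align the Day 16 to 22 labels for the daily checks with the existing rule that they cover the first week of OLE dosing after Visit 4.

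Visit 5 would then fall on Days 19–20, 20–21, 21–22 or 22–23 for a Visit 4 on Day 15, 16, 17 or 18. The latest, Day 23, is 26 − 23 = 3 days before the earliest Visit 6.

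The wording changes are in the synopsis (design and procedures), the OLE schematic footnote, Sections 4.1, 8.1.2 (including the day labels in Table 8.1.2-2), 9.1.2.1, 9.1.2.2 and 9.2.11, and Appendix 1. The SAP covers pilot patients only and needs no change.

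No visit, procedure or blood draw is added. The cost is a second anchoring rule in the OLE and a Visit 5 spread over Days 19 to 23. The change places the visit on the first or second full-dose day. It does not secure post-dose or steady-state tests, because the protocol does not time the Visit 5 ECG or laboratory draw against dosing.
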